Aim 1: Efficacy. Our sample size estimates utilize methods developed specifically for non-inferiority trials.72 In a non-inferiority trial, the null hypothesis (H0) is that the new treatment is inferior to the standard treatment, and the alternative hypothesis (HA) is that the new treatment is not inferior to the standard treatment. "Not inferior to" is defined by the non-inferiority margin, δ . Here, we set $\delta = 2\%$, based on a clinically meaningful difference in average weight loss between the two treatment arms. This means that if the Get Social condition loses up to 2% less weight on average than the Traditional condition, we will consider the Get Social condition to be non-inferior to the Traditional condition. If the Get Social condition loses >2% less weight then it will be considered inferior to the Traditional condition. Thus, adequate power for clinical non-inferiority requires a sample size such that there is better than 90% probability that the lower limit of the confidence interval lies above $-\delta$, if the true effect size is zero or above. We estimated SD=5.5% based on our previous, fully powered randomized trial.28 With alpha=0.05, and δ =2%, we have 90% power to conclude that the Get Social condition is not inferior to the Traditional condition with 131 participants per arm. Accounting for 20% attrition, we will enroll 328 participants total (164 per arm). We considered adjusting the sample for intraclass correlation but previous research shows that weight loss does not cluster among members of weight loss treatment groups.1 We do not believe that the social influence in online groups will be stronger in the Get Social condition. Studies of social influence suggest that team-based activities or recruiting relatives or friends can lead to weight loss clustering but we will not be using such an approach.1 That said, we do believe that after the intervention, peer-to-peer engagement may continue for longer because participants will continue to have a channel by which to communicate with one another. They will also have the opportunity to collect additional social ties outside of the intervention which may be the source of social support, but this is likely to vary greatly across participants (not within treatment groups) and we do not have evidence that such ties will exert social influence of the magnitude of team-based activities and closer ties (i.e., relatives, friends). Secondary outcomes. For the secondary outcomes, we calculated the non-inferiority margins so that we have 90% power to detect given N=131 per arm, setting α=0.05, and using observed SDs from the literature. For change in kcal/day energy intake at 12 and 18 months, we have 90% to detect that Get Social is not inferior to the Traditional condition with a non-inferiority margin of 182 kcal/day with SD=500 kcal/day.28,56 For change in moderate-to-vigorous intensity physical activity minutes per day at 6 and 12 months, the non-inferiority margin is 9.2 minutes/day with SD=25 minutes/day. For percent weight loss at 12 months, the non-inferiority margin is 2.2% with SD=5.5%.28 If weight losses are more variable at 12 mos than 6 mos, the detectable non-inferiority margin is 3.0% with SD=8.0%.57 Power calculations were conducted using PROC POWER in SAS.73,74

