
Aim 2: Cost. With N=131 available per arm (N=262 total) and α =0.05 we have 80% power to detect differences in mean cost per participant of 0.35 SDs. For example, if the SD for cost is \$100, then we have 80% power to detect differences in mean cost per participant of \$35.

Aim 3: Predictors (exploratory). With N=131 available per arm (N=262 total) and α =0.05 for continuous predictors we have 80% power to detect correlations of 0.243 with 12-month percent weight loss. With N=131 available per arm (N=262 total) and setting α =0.05, for categorical variables, detectable differences in mean percent weight loss depend on the proportion of the predictor in the sample. For a predictor with 50% prevalence (i.e., n=65 and n=66 with vs without the characteristic), we have 80% power to detect differences of 0.49 SDs. For predictors with 33% prevalence, we can detect differences of 0.52 SDs. For predictors with 20% prevalence, 0.62 SDs, and for predictors with 10% prevalence (i.e., n=13 vs n=118), 0.82 SDs. For estimated SD=5.5% for 12-month percent weight loss, this indicates differences of 2.7%, 2.9%, 3.4%, and 4.5% weight loss, respectively. Sample size calculations for Aims 2 and 3 were conducted using Stata.

For EACH Participant Population State Describe the Study Population(s): [Describe the participant population(s) including gender, ethnicity, income, level of education and age range.]

We will be recruiting from a representative population of individuals that live or work around Worcester MA and Storrs CT. We are recruiting men and women of all ethnicities, income and education levels between the ages of 18 and 65. Thus far we have had less success recruiting minorities and men and have put additional effort towards that goal. We will recruit participants in 9 waves off set by 2-3 months each. Waves 1-6 were recruited and carried out at UMass and waves 7-9 will be recruited and carried out at UConn.

We will also collect intervention delivery and feedback data from the interventionists. Interventionists are trained in the delivery of the DPP and are set up as consultants.

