Participants will complete a telephone screening, an in-person baseline, and an online webinar (described above). Eligible participants will then be randomized to one of two 12-month weight loss interventions: online (Get Social) or in-person (Traditional). Follow-up assessments will occur at 6- and 12-months.

Randomization: Randomization will take place after the baseline procedures are complete once we've determined eligibility. Participants will be randomized to the Get Social or the Traditional condition. We will randomize 36-40 participants for each recruitment wave, for a goal of approximately 18 per condition. Participants will be randomized 1:1 to the two study conditions in randomly permuted blocks of size 4 and 6 using the ralloc program in Stata Randomization and will be stratified by gender (male vs. female) and baseline BMI (27.0-34.9 vs. 35.0-45.0). The randomization list was generated at the start of the study before randomization. The list is managed by the program director. Once a participant has been determined to be eligible, the program director will assign each participant to the next open assignment on the list. The program director will then tell the research assistant who will reach out to participants to inform them via e-mail of the condition assignment.

Orientation-Visits:

- Traditional participants: This in-person group will last 1 hour and will include training on The first session of the intervention will be extended from 1.5 hours to 2 hours in order to provide time for the orientation which will cover: -My Fitness Pal, an overview of their participation, and study goals. My Fitness Pal is an app that can be used to track diet and physical activity. It can be used on a computer or mobile app. Participants will receive their study goals for weight loss (1-2 lbs. per week), diet, and physical activity. The weight loss goal is approximately 7% weight loss over a 12 month period. This orientation may be completed on an individual in-person basis or phone for people unable to attend the group, though this option won't be encouraged. The weight loss goal is provided in the My Fitness Pal app. –The orientation group is led by the interventionist, a post-doctoral fellow, and a research assistant. and research assistants.

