We will compare total intervention costs per participant and total intervention costs per pound lost by treatment condition. We will conduct sensitivity analyses to estimate the range of costs after varying the inputs (e.g., time spent on Twitter by participants, staff pay across settings and based on qualifications and training). We will also examine administrative, interventionist, and participant costs by treatment condition. Assuming a normal distribution of total costs per participant, we will first compute t-tests comparing the average cost per participant across treatment conditions. We will test the null hypothesis of no difference between groups using a two-sided test and α =0.05. If total cost per participant is not normally distributed, a non-parametric approach using the Mann-Whitney test for median comparisons will be used. If participant characteristics are found to differ according to treatment allocation/condition, multivariable models will be used to adjust for the potential confounding effects of these characteristics. Assuming a normal distribution of total costs per participant, multivariable linear regression models will be used. If not normal, we will identify appropriate transformations (e.g., logarithm, square root) for the cost variable.

Exploratory outcomes (treatment retention, acceptability, and burden)

We will compare treatment retention (percent retained in treatment, i.e., percent who has not dropped out of treatment) and ratings of acceptability and burden (measured on 5-point Likert scales) across treatment conditions using χ^2 tests.

Predictors of weight loss in the Get Social condition (exploratory)

Bivariate associations between each potential predictor of weight loss (e.g., engagement, age, sociability, neuroticism, openness, smartphone and online social network use) and percent weight loss at 12 months will be examined among participants in the Get Social condition using linear regression models. Multivariable predictors of percent weight loss at 12 months will be estimated using linear regression models. Variables will be added to the model one at a time, in order of magnitude of the crude effect estimate (largest to smallest; p<0.05) associated with the outcome. The final model will be selected based on consideration of effect estimates, 95% confidence intervals, and Akaike information criterion (AIC).

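### The 5-point acceptability and burden ratings are compared with chi-square tests that, on the plain reading, ignore the ordering; an ordinal analysis would gain power and give a direction and size

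*Protocol*

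**What the plan says.** The Data Analysis section of the Protocol has a paragraph headed "Exploratory outcomes (treatment retention, acceptability, and burden". It applies one method, the chi-square test, to two kinds of outcome. Percent retained is binary. The others are "ratings of acceptability and burden (measured on 5-point Likert scales) across treatment conditions". The paragraph does not mention a trend or rank version of the test, grouping of the five categories, an effect measure, an alpha or a power figure.

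The SAP covers the preliminary analysis, the primary and secondary non-inferiority outcomes, and cost. It does not mention retention, acceptability or burden, so the Protocol sentence is the only plan for these ratings.

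The Cost paragraph of the same Protocol section already provides for a Mann-Whitney test if cost per participant is not normally distributed. A rank method is therefore not foreign to the plan.

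**The concern.** The Pearson chi-square statistic for two arms by five categories does not change if the five columns are reordered. It asks whether the two distributions differ in any way. The natural question here is narrower: does one arm rate its programme as more acceptable, or less burdensome? That is a shift along an ordered scale. An unordered test spreads its sensitivity over 4 degrees of freedom when the alternative of interest needs 1, and a significant result does not say which arm did better or by how much.

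The Protocol's opening rationale names patient and provider burden as a main reason why lifestyle programmes are not widely disseminated, and argues that online delivery removes patient barriers. The ratings bear on that argument. An inefficient test could miss a real burden advantage for Get Social, or a real deficit in its acceptability.

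**Working it through.** **Inputs from the documents**
- Evaluable n: "With N=131 available per arm (N=262 total". This is the 12-month figure used in the power statements and is assumed here for the ratings.
- Enrolment: "Accounting for 20% attrition, we will enroll 328 participants total (164 per arm"; allocation: "Participants will be randomized 1:1 to the two study conditions".
- Alpha: "using a two-sided test and α =0.05", stated for cost and assumed for the ratings.
- Benchmark effect: "we have 80% power to detect differences in mean cost per participant of 0.35 SDs", also stated for cost and borrowed here as a reference point.

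**Reproducing the plan's own figures**
- Primary outcome, margin 2%, SD 5.5%: non-central t power at one-sided 0.05 is 90.2% with 131 per arm and 89.96% with 130. So 131 reproduces.
- Enrolment: 131 / 0.80 = 163.75, rounded up to 164 per arm.
- Cost benchmark: noncentrality = n x d² / 2 = 131 x 0.35² / 2 = 8.02. Two-sided 1-df power is 80.9%, against the stated 80%.

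**Price of the extra degrees of freedom alone**

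The 5% critical values are 3.841 (1 df) and 9.488 (4 df). At the same noncentrality of 8.02, power falls from 80.9% to 60.6%. At 7.85, where the 1-df test has 80%, the 4-df test has 59.5%.

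**Five-category calculation**

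The rating distribution and the shift are assumptions. Three reference distributions were used (percent in categories 1 to 5):
- Flat: 20/20/20/20/20
- Skewed: 5/10/20/35/30
- Very skewed: 3/5/12/30/50

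For reference cells p_k with normal cut-points c_k, the other arm has q_k = Φ(c_k − d) − Φ(c_{k−1} − d), where d is the latent shift in SD. Let m_k be the mean of p_k and q_k.
- Unordered test: λ4 = n Σ [(p_k − m_k)² + (q_k − m_k)²] / m_k
- Rank-score test: λ1 = n [Σ s_k (q_k − p_k)]² / (2V), where s_k are midrank scores and V is their variance under m_k
- Power = P(non-central χ² with 4 or 1 df exceeds 9.488 or 3.841)

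Example, flat ratings and d = 0.35: q = 0.117, 0.157, 0.188, 0.227, 0.312. This gives λ4 = 7.02 and λ1 = 6.96. Nearly all the signal lies in the single ordered component, so the other 3 df add almost nothing. Power is 54.1% against 75.1%.

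Power at 131 per arm, 4 df vs 1 df (loss in points, from unrounded values):

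| Shift | Flat | Skewed | Very skewed |
|---|---|---|---|
| 0.10 SD | 8% vs 12% (4) | 8% vs 12% (4) | 8% vs 11% (3) |
| 0.20 SD | 19% vs 33% (14) | 19% vs 32% (13) | 17% vs 29% (12) |
| 0.35 SD | 54% vs 75% (21) | 52% vs 73% (21) | 46% vs 67% (21) |
| 0.40 SD | 67% vs 85% (18) | 65% vs 83% (19) | 58% vs 78% (20) |
| 0.50 SD | 87% vs 96% (10) | 85% vs 95% (11) | 78% vs 92% (14) |
| 0.60 SD | 96% vs 99% (3) | 95% vs 99% (4) | 91% vs 98% (7) |

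**Cross-check by simulation**

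Pearson chi-square was compared with a tie-corrected Wilcoxon test under proportional-odds shifts, with 131 per arm, 20,000 trials per scenario and four assumed rating distributions. The loss was 6-7 points at a common odds ratio of 1.25, about 18 at 1.5, 22-23 at 1.75, 17-20 at 2.0 and 6-9 at 2.5. Type I error was close to 5% for both tests. With a difference in spread only, the ranking reversed: 94% for chi-square against 6% for the rank test.

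**The case against.** Several objections have force.

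- **The outcomes are exploratory.** They appear in none of Aims 1 to 3 and in no power statement. This stands, and it caps the importance of the point.
- **The test is not wrong.** Its type I error is about 5%. A reader might infer that the comparison is invalid, but the issue is efficiency and interpretability only.
- **The loss is not a constant.** A reader might infer a fixed loss of about 20 points. The documents give no expected effect or rating distribution for these outcomes, 0.35 SD is stated only for cost, and the table shows losses of 3-7 points at 0.10 and 0.60 SD. Planned intervention time differs greatly between arms (750 against 1980 minutes in the Time Commitment table). If burden ratings differed strongly as a result, either test would detect it.
- **An ordinal test has a cost.** It is tempting to call the swap free. If opinion of a Twitter programme were polarised around a similar centre, a rank test could miss it where the unordered test would not. This stands and shapes the fix.
- **The text does not force a 2 x 5 unordered table.** A trend chi-square or dichotomised ratings could have been meant. Neither is stated, so the unordered reading is the plain one but still an inference. If something else was intended, the text needs an edit to say so.
- **Nothing says a null result would be read as favourable.** A reader might suppose that finding no difference in acceptability or burden would count for the new modality. The documents frame only weight, diet and activity as non-inferiority outcomes, so that reading is not supported. Nor does the plan prevent reporting the rating distributions by arm, which would show direction even though the test does not.

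**Conclusion.** The concern holds as a minor improvement. Followed as written, the plan tests ordered ratings with a valid method that ignores their order and yields no direction or effect size. The power cost is about 18-21 points for shifts of 0.35-0.40 SD and falls away on either side, to 3-7 points at 0.10 or 0.60 SD. These figures rest on 131 evaluable per arm, two-sided 0.05, a pure latent normal shift and the three assumed rating distributions. None of these is stated for the ratings themselves. Chi-square is appropriate for percent retained, and no conclusion on weight loss, cost or predictors is affected.

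**What to change.** In the Protocol paragraph on exploratory outcomes, and in a matching SAP entry:
- Analyse each 5-point rating with a Wilcoxon rank-sum test or a proportional-odds model.
- Report an effect estimate with a 95% CI, such as the common odds ratio or the probability that a participant in one arm gives a higher rating than one in the other.
- Tabulate all five categories by arm, so that a polarised response is visible even if the rank test is null.
- Keep chi-square for percent retained.
- If a trend test or grouped categories were intended, say so and define them.

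The cost is a sentence or two and no extra data. What is given up is sensitivity to spread-only differences, which the table partly covers. If the ratings have already been seen by arm, label the ordinal analysis as added later.

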Aim 1: Efficacy. Using a randomized trial (N=328), we will test whether a lifestyle intervention delivered via an online social network (Get Social) will result in a mean percent weight loss at 12 months that is not appreciably worse than the gold-standard in-person group-based lifestyle intervention (Traditional), i.e., the social network arm will not lose on average 2% less than the in-person arm. Secondary non-inferiority outcomes include weight loss at 12 months, and dietary intake and physical activity at 6- and 12-months.

Aim 2. Cost Analyses. To determine whether the lifestyle intervention delivered via an online social network will cost less per participant than in-person delivery. We hypothesize that the Get Social condition will cost less per participant than the Traditional condition.

Aim 3. Predictors (exploratory). We will test predictors of weight loss in the Get Social condition including engagement, age, sociability, neuroticism, openness, and smartphone and social network use. We hypothesize that people who are younger, more sociable, engage more on the social network, higher in neuroticism/openness, and heavier overall smartphone and social network users will lose more weight in the Get Social condition.

For EACH Participant Population State the Number of Participants to be Enrolled and Screened, if applicable: [State the total number of participants to be enrolled and, if enrolling more than one participant population, describe the total enrollment for each. Tip: consider attrition and the number of participants who may fail screening. Use of a range may provide flexibility.] Note that the range must be justified in the **Justification of Sample Size section below**.

The total number of subjects that will be recruited will be 328 randomized participants and 6 interventionists. It is estimated that we will screen 700 participants to achieve this recruitment goal.

Justification of Sample Size: [For qualitative and pilot studies, describe how the proposed sample size is appropriate for achieving the anticipated results. For quantitative studies, provide a power analysis that includes effect size, power and

level of significance with references for how the sample size was determined. Explain the rate of attrition and possible number who fail the screening, with references as appropriate.]

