Participants will complete follow-up visits at 6- and 12-months. The visit will last 1 hour and will include a weight measurement, blood pressure reading, three 24-hour diet recall interviews, and repeated baseline measures. The online survey containing the measures will be e-mailed to participants 1 week prior to the scheduled follow-up visits.

Time Commitment:

Visit	GS Condition	TC Condition
	(in minutes)	(in minutes)
Telephone Screening (20 min)	20	20
Baseline (210 min total)	210	210
Visit (90 min)		
2 at-home dietary recalls (60 min)		
Online survey (60 min)		
Webinar (60 min)	60	60
Orientations	180	

GS: individual orientation (60 min)		
GS: group orientation (120 min)		
TC: group orientation (60 min)		
Intervention	750	1980
GS: approx. 35 min/week 8 weeks, 14 min/week		
for 16 weeks, 8 min/week for 28 weeks (12.5 hrs)		
TC: 22 1.5 hr groups (33 hrs)		
6-month (150 min total)	150	150
Visit (30 min)		
2 at-home dietary recalls (60 min)		
Online survey (60 min)		
12-month (150 min total)	150	150
Visit (30 min)		
2 at-home dietary recalls (60 min)		
Online survey (60 min)		
Total	1520 minutes	2630
	(approx. 25 hrs)	2570 minutes
		(approx. 434
		hrs)

Interventionist data collection:

The interventionists provide the following information, some of which will be used in the analysis:

- Weekly timesheets for invoicing their time (these hours are used to calculate time/cost needed to deliver the intervention aim 2).
- A 10 minute survey at the end of each 6-month phase for each wave used to gather interventionist feedback.

Measures

Data Collected	List of Measures	Baseline	During	6	12	Method
			Intervention	Months	Months	
BMI	Height	Х				REDCap
	Weight	Х	X (weekly)	Х	Х	REDCap
Medications	Brief Medication Questionnaire ¹⁰	Х		Х	X	REDCap
Blood pressure	Blood Pressure	Х		Х	Х	REDCap
Demographics	Income, employment, marital status, race/ethnicity, household composition*	Х				REDCap
Medical History	Assesses exclusionary medical conditions*	Х				REDCap
Personality factors neuroticism/ openness	Ten-Item Personality Inventory (TIPI) ¹¹	Х				REDCap
Binge Eating Disorder	SCID Interview ¹² for BED	Х				Interview
Physical Activity	Arizona Physical Activity Questionnaire ¹³	Х		Х	X	REDCap
Sleep Quality	STOP ¹⁴	Х		Х	Х	REDCap
	Insomnia Severity Index ¹⁵	X		X	X	REDCap
	Pittsburgh Sleep Quality Index Questions ¹⁶	Х		Х	X	REDCap

	History of sleep apnea diagnosis*	X		X	X	REDCap
	Previous or current treatment for sleep apnea*	X		X	X	REDCap
Depression	BDI ¹⁷	Х		Х	X	REDCap

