Chronic Pain	Brief Pain Inventory ¹⁸	Х		X	Х	REDCap
Quality of Life	EQ-5D-3L ¹⁹	X		X	Х	REDCap
Contamination	Weight-loss related social media use*	X			X	REDCap
Social media use	Social Media Use*	Х		Х	Х	REDCap
Dietary recall	3 24hr recalls (ASA24- Automated Self- Administered) ²⁰	X (3)		X (3)	X (3)	Online
Social support for weight management	WMSI ²¹	X		X	X	REDCap
Measure time spent on Twitter	Phone or app tracking		X			REDCap
Group engagement on Twitter	Engagement in group		X	X	X	Twitter
Treatment receipt	Questions each week related to intervention*		X			REDCap
Intervention acceptability and burden	Questions given at 6m follow-up* and time spent data extraction from getsocial.com			X	X	REDCap
Interventionist Feedback (Interventionists only)	Interventionist Survey*			X		REDCap

* Investigator-derived items

Data Analysis: [For all studies, specify the analytic techniques the researcher will use to answer the study questions. Indicate the statistical procedures (e.g. specific descriptive or inferential tests) that will be used and why the procedures are appropriate. For qualitative data, specify the proposed analytic approaches.]

Preliminary analysis

Baseline participant characteristics will be examined by condition. If groups differ on certain characteristics, these variables will be included as covariates in the primary analyses. Other preliminary analyses include assessing patterns of missing data, dropout rates, distributional properties of dependent measures, and correlations among outcome measures. A series of sensitivity analyses will be performed to examine the extent of potential bias by assuming the participants who dropped out are (i) missing completely at random (i.e., independent of the outcome), (ii) are responders to the intervention, or (iii) are non-responders to the intervention. Multiple imputation to impute missing data will be used if more than 5% of data are missing.

Primary non-inferiority outcome

We will model percent weight loss at 12 months using a linear regression model framework, with percent weight loss as the dependent variable and study condition as the independent variable. Test of the intervention condition indicator will provide a statistical test of the intervention effect and the estimated coefficient, along with the

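### The Aim 3 multivariable model lets engagement, measured only after randomisation, compete with baseline traits, so trait coefficients may lose whatever part acts through engagement

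*Protocol*

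**What the plan says.** Aim 3 of the Protocol expects that "people who are younger, more sociable, engage more on the social network, higher in neuroticism/openness", as well as heavier smartphone and social network users, will lose more weight in Get Social. The Data Analysis section on predictors is labelled exploratory and has two steps.

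- **Single-predictor step.** It examines "Bivariate associations between each potential predictor of weight loss (e.g., engagement, age, sociability, neuroticism, openness, smartphone and online social network use", each against 12-month percent weight loss, within the Get Social arm.
- **Multivariable step.** "Multivariable predictors of percent weight loss at 12 months will be estimated using linear regression models". The entry rule is: "Variables will be added to the model one at a time, in order of magnitude of the crude effect estimate (largest to smallest; p<0.05". The stopping rule is: "The final model will be selected based on consideration of effect estimates, 95% confidence intervals, and Akaike information criterion (AIC".

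Neither step separates the candidates by when they are measured. The Protocol's Measures table does show the timing. "Group engagement on Twitter" is marked during the intervention, at 6 months and at 12 months, and not at baseline. The "Ten-Item Personality Inventory (TIPI") is marked at baseline only. Social media use is marked at baseline, 6 and 12 months, and the analysis section does not say which measurement is the predictor.

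The Protocol's background paragraph on the pilot work gives the purpose: to learn which people the online format suits. No engagement window, time lag, mediation analysis or baseline-only multivariable model is described. The SAP has no predictor section, so it neither changes nor repairs this.

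**The concern.** Two problems follow from treating engagement as one more trait.

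First, engagement is a plausible route by which sociability or heavy social media use would lead to weight loss. A regression that contains both the trait and engagement estimates only the part of the trait's effect that bypasses engagement. Someone choosing a format for a new patient knows the trait but cannot know future engagement. For that decision the total association of the trait is the relevant quantity.

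Second, engagement accumulates over the period in which weight is lost. Its association with 12-month loss may run from weight to posting, or both may share a cause. The Protocol's withdrawal rules show how a shared cause could arise. A participant may leave all intervention activity and still attend the final assessment. A participant who becomes pregnant is withdrawn from the intervention but may still be assessed.

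At stake is the interpretation of the multivariable model: a trait could look unimportant there, and engagement could be read as a driver of weight loss. The main trial result is not at stake.

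**Working it through.** **1. Inputs from the Protocol.** Justification of Sample Size, Aim 3: n = 131 in the Get Social arm, α = 0.05, 80% power, detectable correlation 0.243, SD of 12-month percent weight loss 5.5%. The documents give no path strengths between traits, engagement and weight loss, so those below are assumptions shown as ranges.

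**2. The plan's own figure.** By the Fisher z approximation, two-sided:

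r = tanh[(1.960 + 0.842)/√(131 − 3)] = tanh(0.2476) = 0.2427.

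This reproduces 0.243; power at 0.243 is 80.1%. With n = 262 the result would be 0.172, so the stated figure is for one arm and for a simple correlation, which is the single-predictor step.

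**3. Trait coefficient with and without engagement.** Use standardised variables. Let *a* be the path from trait to engagement, *b* the path from engagement to weight loss given the trait, and *c* the direct path from trait to weight loss.

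- Without engagement in the model: coefficient = *c* + *ab*, set to 0.243.
- With engagement in the model: coefficient = *c* = 0.243 − *ab*.
- Crude association of engagement: *b* + *ac*.

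The coefficients below are exact. The percentages come from 4,000 simulated samples of n = 131 per row.

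| *a* | *b* | Trait coefficient with engagement | Share removed, *ab*/0.243 | Engagement passes crude p<0.05 | Trait p<0.05, engagement in model |
|---|---|---|---|---|---|
| 0.2 | 0.3 | 0.183 | 25% | 98% | 58% |
| 0.2 | 0.5 | 0.143 | 41% | 100% | 46% |
| 0.3 | 0.3 | 0.153 | 37% | 99% | 43% |
| 0.3 | 0.5 | 0.093 | 62% | 100% | 22% |
| 0.5 | 0.3 | 0.093 | 62% | 98% | 16% |
| 0.5 | 0.5 | −0.007 | 103% | 100% | 5% |

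Without engagement, the trait reached p<0.05 in 80% to 81% of samples in every row. On AIC alone, with engagement already in, the trait was kept in 78% of samples in the first row and 17% in the last.

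In weight terms, 0.243 × 5.5 = 1.34 percentage points per SD of the trait. This falls to 0.183 × 5.5 = 1.01 in the mildest row and to about 0 in the last.

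**4. Would engagement be in the model?** Only if its crude p<0.05. An engagement correlation of 0.243 or more passes at least 80% of the time, by step 2. In the rows above its crude association *b* + *ac* runs from 0.3 + 0.2 × 0.183 = 0.34 to 0.5 + 0.2 × 0.143 = 0.53, hence 98% to 100%. On a standardised scale it would also enter ahead of the trait.

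**5. Reverse or shared causation.** Suppose engagement has no effect on weight. Let it follow early weight loss with correlation *g* (assumed 0.2 to 0.5), and let early loss correlate ρ with 12-month loss (assumed 0.6 to 0.8). The correlation of engagement with the outcome is then *g*ρ, from 0.2 × 0.6 = 0.12 to 0.5 × 0.8 = 0.40. In 20,000 simulated samples of n = 131 per setting, p<0.05 occurred in 28% to nearly 100%. This shows what the planned regression cannot distinguish. It does not show that the mechanism operates in this trial.

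**The case against.** The strongest reply is that the single-predictor step already gives what is needed. Engagement is absent from those regressions, each trait keeps its total association, and the Protocol's 0.243 refers to that analysis. This stands. A reader might infer that Aim 3's hypotheses about younger, more sociable or heavier users would be rejected merely because engagement is in the model. The documents do not support that: they do not say that the hypotheses are judged on the multivariable coefficients, and a trait with a total effect of 0.243 would be found about 80% of the time in the first step. It would also be wrong to compare an engagement-adjusted coefficient with 0.243 as if the two were the same quantity.

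The masking is also conditional: engagement must pass the crude screen, and stepwise entry lets the analyst see a trait coefficient shrink. This too stands, but the Protocol's own hypothesis makes entry likely, and no rule says what to do when the coefficient shrinks.

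A reader might further infer that engagement is a result of weight loss. Nothing in the documents shows this. They show only that the analysis would not reveal it.

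Finally, the aim is exploratory and speaks of predictors, and reporting engagement as a correlate is no error. That is fair for engagement on its own. It does not answer the mismatch between a multivariable model containing post-randomisation behaviour and a purpose that concerns characteristics known beforehand. What remains missing is a joint model of baseline variables.

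**Conclusion.** The concern holds for the multivariable step of Aim 3 and is minor. If engagement enters, trait coefficients lose the part that works through it. Under the assumed paths that is 25% to all of a 0.243 effect, and the chance of p<0.05 falls from about 80% to between 58% and 5%. The direction follows from the model whenever a trait with a positive total effect acts positively through engagement. The size rests entirely on assumed paths and should not be quoted as a single figure. The possibility of reverse or shared causation is a lack of protection in the plan, not a demonstrated bias. The single-predictor results for traits are sound on this point, and the primary, secondary and cost results are untouched.

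**What to change.** Add a short predictor section to the SAP, which has none:

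1. Build the multivariable model that addresses whom the format suits from baseline variables only: age, personality, and baseline smartphone and social media use. State which baseline item represents sociability and which represents smartphone use, since the Measures table names neither as a separate row.
2. Report engagement with 12-month percent weight loss in a separate model, with its measurement window stated, and describe the result as an association.
3. As an added sensitivity analysis, not a replacement, relate engagement in months 1 to 6 to weight change between the 6- and 12-month visits. Visit weights suit this better than the weights between visits, which Get Social participants report by e-mail.

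This uses data that the Protocol already plans to collect: tweets are gathered continuously, and weight is measured at both visits. The cost is the new SAP text, one extra model and the sensitivity analysis. The sensitivity analysis is noisier, leaves out weight loss in the first six months, and reduces but does not remove confounding, because people who do well early may both post more and keep losing.
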